Our preliminary data⁴⁰ suggest that DRA treatments for destructive behavior like those described below consistently produce at least 85% reduction in baseline rates of destructive behavior after 1-4 DRA sessions. Based on these results, we will set the length of our short-duration condition to approximately 4 sessions. RaC predicts that this short duration of DRA will produce high magnitudes of resurgence during a resurgence test but less resurgence than predicted by BMT. We will compare this short-duration condition with a moderate-duration condition (i.e., approximately 8 sessions of DRA) and an extended-duration condition (i.e., approximately 32 sessions of DRA). RaC predicts that, relative to the short-duration condition, the moderate-duration condition will reduce resurgence only slightly, but the extended-duration condition will reduce resurgence considerably. Each of three durations of DRA (i.e., short, moderate, and extended) will

consist of three phases, a baseline phase, a treatment phase (i.e., DRA), and an extinction phase (i.e., resurgence test). We will conduct this progression of phases three times per participant (i.e., one progression for each duration of DRA), with each progression occurring in a novel stimulus context (i.e., three contexts per participant assigned to conditions randomly), to minimize carryover effects.

Baseline- and DRA-progressive-interval assessment. We will conduct a brief, progressive-interval assessment (PIA) to identify a sufficiently dense schedule of reinforcement for use in subsequent baseline and DRA sessions. The assessment will be identical to the functional-analysis condition with the highest rates of destructive behavior (e.g., the attention condition of the functional analysis for attention-reinforced destructive behavior) with the following exceptions: (a) initially, destructive behavior will be reinforced on a dense schedule of reinforcement, (b) periods of nonreinforcement will begin and increase after every two reinforcer deliveries, and (c) the assessment will end after two reinforcement deliveries corresponding to a nonreinforcement period of 180 s or if untoward effects are observed (i.e., a burst of destructive behavior or negative emotional responding). We will use the results of the PIA to select a dense schedule of reinforcement that does not produce bursts of destructive behavior nor negative vocalizations for use in the baseline and DRA phases.

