4.3 Number of Subjects

A. Total Number of Subjects

We conservatively estimate at least 60% of patients receiving clinical treatment in our program will meet the inclusion criteria. During the project, we will recruit 22 (12 for study 1 and 10 for Study 2) and retain 20 children with severe destructive behavior. We expect 10% attrition.

B. Total Number of Subjects If Multicenter Study

Not Applicable

C. Feasibility

We will recruit 22 and retain 20 children with severe destructive behavior from the Severe Behavior Program. We will recruit 12 and retain 11 children for Study 1, and we will recruit 10 and retain 9 children for Study 2. We conservatively estimate at least 60% of patients will meet the criteria (n = 45 per year available; eight per year needed, maximum). The research team will communicate the recruitment plan to all case managers in the Severe Behavior Program so that case managers can recommend relevant participants. The principal investigator and research staff will meet to discuss recruitment status and resolve any issues related to recruitment.

Additionally, the DDDC has 10 classes with a class size between 5 and 8 patients. Thus, the DDDC has between 50 and 80 patients at a given time. The majority of patients have a diagnosis of ASD, and a large minority of patients are reported to display destructive behavior. We expect that roughly 5-10 patients will be appropriate for the study, and recruitment is deemed feasible.

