Provide protocol specific findings justifying this determination:

[Return to Section 1.](#)

3 Research involving children under 21 CFR §50.52/45 CFR §46.405 (Check if "Yes". All must be checked)

The research involves greater than Minimal Risk to subjects.
Provide protocol specific findings justifying this determination: There is a potential for child, therapist, and parent/caregiver injury as a result of the child's problem behavior. Problem behavior such as aggression, property destruction, or self-injury may be occasioned by presenting difficult demands, restricting access to preferred items, or activities or restricting access to caregiver attention. The risks may be greater during the extinction challenge/relapse test. All therapists participating in the study have received formal training on how to appropriately and safely block problem behavior in a manner that minimizes these risks. If the child engages in problem behavior that may result in injury to the therapist, the therapist will have the option to wear protective equipment during the assessment (e.g., arm guards, chest and shoulder pads, etc.). If the child engages in problem behavior that may result in injury to the caregiver, the caregiver will have the option for a therapist to come in and assist them or to terminate the session. If the child's problem behavior appears to escalate to unsafe levels, the session will be ended and clinically-approved measures will be implemented to ensure the safety of the child. There is also a risk of loss of confidentiality. The loss of confidentiality is unlikely due to the use of a secured network hard drive to store all personal identifiers.

The research presents the prospect of direct benefit to the individual subjects.
Provide protocol specific findings justifying this determination: Participants may receive treatment services for their destructive behavior and be taught replacement behaviors based on the results of the functional analyses. A reduction in destructive behavior may be a result of basing treatment on the functional analyses.

One of the following is true. (Check box that is true)

- The risk to children is presented by an intervention or procedure that holds out the prospect of direct benefit for the individual subject.
- The risk to children is presented by a monitoring procedure that is likely to contribute to the subject's well-being.

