We will interview the primary caregiver(s) to determine how often and under what conditions the participant's destructive behavior results in physical harm to self or others. We will use this information to ensure that no participant is exposed to more risk during participation in this project than in the natural environment. We will always block or use protective equipment (e.g., arm splints) to prevent self-injurious behavior or aggression directed toward vulnerable organs (e.g., eye-gouging). Potentially harmful effects of severe head banging (e.g., detached retinas, concussions) will be mitigated by conducting sessions in a well-padded therapy room or, if necessary, having the individual wear a padded helmet. We will terminate sessions if self-injurious behavior results in reddening of the skin or frank bleeding. Further occurrences of self-injurious behavior will be blocked or prevented with protective equipment until the tissue has fully healed or the child has been examined by a nurse or physician and medically cleared to continue participation. In the Severe Behavior Program, we will routinely collect data on all adverse events (e.g., patient-to-patient aggression, staff or patient injuries), regardless of severity level. If we observe soft-tissue symptoms, they will be monitored daily and documented with images in medical progress notes until the symptoms resolve. If symptoms persist or are serious and acute, we will have a physician evaluate the child if one is immediately available, or if not, we will bring the child to a local emergency room. All adverse events will be reviewed during monthly meetings. Additionally, any unexpected or serious adverse event will be reported to the IRB, and we will respond to the adverse event as advised by the IRB. The emergence of unexpected or serious adverse events related to this study may result in removal of the participant from the study.

B. Data/Safety Monitoring Board Details

One of the postdoctoral fellows on this project will serve as the data coordinator and track the IRB application, and ensure that study personnel are using only the latest version of the protocol. In addition, this postdoctoral fellow will conduct an annual audit to ensure compliance with all IRB policies and procedures, including review of consent forms to make certain that consent forms are up to date and

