## Statistical Plan

### Experiment 1

We will collect interobserver agreement on at least 33% of all sessions and ensure that the second data collector is blind to the study aims and hypotheses on one half of those observations. For Exp. 1, we will compare magnitudes of resurgence for the three treatment durations observed during the first five sessions of each resurgence test. We will report findings for each sex, in addition to reporting our aggregated data across sexes. We will apply a general linear model with two within-subject variables (individual session number and treatment duration) and one between-groups variable (treatment-duration sequence). We expect large differences between the extended-DRA condition and the short-DRA condition and a small-to-nonsignificant effect for the other paired comparisons (i.e., short vs. moderate and moderate vs. extended). Finally, model fits and comparisons for RaC and BMT will be conducted.

### Experiment 2

We will compare the prevalence and magnitude of resurgence during this RaC-informed schedule-thinning progression to that observed in the control group. We will calculate odds ratios for the likelihood of resurgence with and without RaC information on a per-case and on a per-schedule-step basis. We will apply Fisher's exact-probability statistic to test the significance of the odds ratios. With a minimum expected reduction in the per-case prevalence of 50% across 12 participants, we estimate a power of 0.89 with alpha=0.05. In addition, on a per schedule-step basis, the power increases to 0.98 with alpha=0.05. We will assess the adequacy of RaC and BMT in describing the data. Because BMT is not equipped to incorporate dynamic changes in DRA, we expect this model to poorly describe the data. RaC, however, easily incorporates such dynamic changes, and we expect the model to provide a good description of the data.

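### Experiment 1 names a repeated-measures linear model but no analysis set or missing-data method; run in its usual form it would drop children who do not finish all three progressions, and could bias the short-versus-extended contrast.

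*SAP*

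**What the plan says.** The SAP (Statistical Plan, Experiment 1) compares resurgence across the three DRA durations as "observed during the first five sessions of each resurgence test". The model is given in one sentence: "We will apply a general linear model with two within-subject variables (individual session number and treatment duration"), plus "one between-groups variable (treatment-duration sequence"). Nothing is said about estimation method, analysis set or missing data.

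Protocol section 1.3 A gives the design: "We will conduct this progression of phases three times per participant", one for each duration, each ending in a resurgence test. The stimulus contexts are assigned to conditions at random. How children are allocated to orders of duration is not stated.

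On attrition, protocol section 4.3 C says: "We will recruit 12 and retain 11 children for Study 1". Section 6.3 A says: "The emergence of unexpected or serious adverse events related to this study may result in removal of the participant from the study". Section 4.4 B lets caregivers remove a child at any time. On the resurgence test, the Section 3 entry of the children's checklist in section 5.5 says: "The risks may be greater during the extinction challenge/relapse test".

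**The concern.** Each child contributes up to 3 durations × 5 sessions = 15 values. A classical repeated-measures general linear model with two crossed within-subject factors needs all of them. A child who leaves after one or two progressions is therefore normally left out whole, together with the resurgence tests already recorded.

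This matters more than usual here for two reasons. The sample is 12, so one child is 8.3% of it. And loss may not be independent of the outcome: the adverse events the protocol describes are largely injuries from destructive behavior, which is also what the resurgence test measures. If children with strong resurgence are the likelier ones to leave, a completers-only analysis describes resurgence in children who stayed through all three tests, and the contrast it estimates can shift. That contrast, short against extended, is the one large effect the plan expects.

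**Working it through.** **1. The plan's own figure.** 12 × (1 − 0.10) = 10.8, rounded to 11 retained. One lost child is 1/12 = 8.3%.

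**2. Effect of losing one child.** Let m be the mean short-minus-extended difference over all 12 children and x the lost child's own difference. The mean of the remaining 11 is (12m − x)/11, so the relative change is (m − x)/(11m). It reaches −10% when x = 2.1m, since (1 − 2.1)/11 = −0.10.

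The sign depends on x. Suppose the other 11 children average 0.50, so that the 12-child mean is (5.5 + x)/12:

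| Lost child's x | 12-child mean | Completers only | Relative error |
|---|---|---|---|
| 1.5 | 0.583 | 0.50 | −14.3% |
| 1.0 | 0.542 | 0.50 | −7.7% |
| 0.5 | 0.500 | 0.50 | 0 |
| 0 | 0.458 | 0.50 | +9.1% |
| −0.5 | 0.417 | 0.50 | +20% |

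**3. Simulation with proportional child effects.** The documents give no effect size or variance for Experiment 1, so every input here is an assumption:
- 12 children, two in each of six orders, with one child lost after a test that is not the last.
- Mean resurgence in the ratio 1 : 0.85 : 0.30 for short : moderate : extended, giving a true difference of 0.70.
- Between-child CV 0.5 to 1.0; within-child log-SD 0.3 to 0.5.

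| Which child is lost | Completers-only result |
|---|---|
| Always the child with the highest non-final test | 0.549 to 0.620; 0.620/0.70 − 1 = −11%, 0.549/0.70 − 1 = −22% |
| Chance proportional to observed rate | about −2% to −8% |
| Random (CV 0.8, log-SD 0.3) | 0.696; no bias |

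Under rate-proportional loss the difference was not understated in 36% to 45% of individual trials.

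**4. Dependence on order.** A second set of simulations removed 8.3% to 10% of children when an early test passed a severity threshold. Assumed mean resurgence as a proportion of baseline was 0.8/0.7/0.3 (large contrast, true difference 0.5) or 0.8/0.7/0.7 (small contrast, true difference 0.1, so percentages are inflated).

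| Order | Large contrast | Small contrast |
|---|---|---|
| Random | −2% to −24% | −4% to −28% |
| Short first | −3% to −29% | −13% to −95% |
| Extended first | −14% to +2% | +4% to +55% |

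**5. Does keeping the completed tests help?** With additive child effects (SD 0.3, residual SD 0.4, large contrast, 10% removal), a random-intercept mixed model on all available tests was compared with completers:

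| Order | Full data | Completers only | Mixed model |
|---|---|---|---|
| Random | 0.498 | 0.469 | 0.501 |
| Extended first | 0.496 | 0.507 | 0.497 |

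In the step 3 settings with worst-case loss, a likelihood fit with unstructured covariance gave 0.688 to 0.706 against the true 0.70. A simpler covariance with common variance recovers only part of the shortfall there, because resurgence was assumed to scale with the child. It was still closer to the full-data contrast than completers only under all three loss rules.

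**The case against.** A reader might infer that the SAP prescribes deletion of incomplete children. It does not. The SAP gives only the model's name and factors, and the same structure can be fitted by likelihood with partial data kept. This stands, and it is why the point concerns an unspecified method and its usual form.

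A reader might also infer that the short-versus-extended difference will be understated. The documents do not support that as a certainty. They do not say which children will leave, after which test, or how orders are allocated; steps 2 and 4 show zero and reversed bias. The reversed averages arise only when every child starts with extended DRA, which fits poorly with a sequence factor in the model. A smaller difference is therefore the likelier direction, no more.

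The link from resurgence to removal can also be questioned. Protocol section 6.3 A first answers injury within sessions, by ending them, blocking or protective equipment. Exclusion (e) in section 4.1 screens out the most dangerous self-injury. Removal is only something that may follow, and the 10% attrition is given no cause. This weakens the worst case but does not rule out outcome-related loss.

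Finally, section 6.1 has data graphed and analyzed for all participants, and section 1.9 A applies structured visual inspection to single-case data. A departed child's tests would still be seen there. That does not repair the group contrast.

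**Conclusion.** The concern holds as a gap with a plausible bias. The SAP leaves open who is analysed and how incomplete children are handled, in a trial of 12 that expects to lose one. If the model is run on completers and loss is related to resurgence, the short-versus-extended contrast is probably too small: by about 2% to 8% when the chance of loss is proportional to the observed rate, and by 11% to 22% only if the most severe child is always the one lost. With random loss there is no bias, only lost precision. All these sizes rest on assumed means, variances and removal rules, and the direction depends on the order of durations.

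Nor should a reader take 11 retained children to mean 11 complete records. Section 1.3 A lets a resurgence test end once behavior is about 90% below baseline for two consecutive sessions, so a test can stop before the five sessions the model uses. That is a separate gap.

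**What to change.** In the SAP's Experiment 1 paragraph:
- State that the model is a likelihood-based (REML) linear mixed model with the planned fixed effects of duration, session number and sequence.
- Use a parsimonious covariance, for example random child and child-by-duration effects, with small-sample degrees of freedom.
- Define the analysis set as every child with at least one resurgence test, including those who leave before finishing all three progressions.
- Report the analysis of children with all three progressions as a sensitivity analysis.
- List each departure with its reason and the last resurgence test completed, and state how children are allocated to orders.

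The cost is SAP wording and a standard software routine, with no additional children, sessions or staff. There are two downsides. The model assumes that missing durations are predictable from the tests the child completed, which is weaker if a child leaves partway through a test. And with 12 children the covariance is estimated imprecisely; a simple structure is more stable but, as step 5 shows, may remove only part of the bias.

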Limitations of DRA. Although highly effective, DRA has a number of limitations¹⁷⁻²¹ that compromise its effectiveness when implemented by caregivers in the natural environment. In the latter stages of DRA, caregivers are trained to implement treatment, and it is critical that they do so with high procedural integrity (e.g., 90% accuracy), which is more likely if the intervention is practical and compatible with their daily routine. Researchers have identified two important practical limitations of DRA that can interfere with accurate caregiver implementation, namely that treated individuals request reinforcement via the FCR (a) at exceedingly high rates (e.g., request to escape every adult directive) or (b) when it is difficult for the caregiver to deliver reinforcement (e.g., requesting attention when a parent is changing an infant sibling). Our research team and others have used reinforcer-schedule thinning procedures to address these limitations and improve the practicality of DRA.^{21,23} Reinforcer schedule thinning involves progressively and systematically reducing the amount of reinforcers available during treatment sessions. This process is conducted in order to prepare the treatment to be practically used when reinforcers cannot always be feasibly delivered. Unfortunately, in the first large study on reinforcer-schedule thinning, we found that DRA was ineffective in 14 of 25 applications when schedule thinning reached a practical endpoint.²¹ In most cases, it was necessary to add a more restrictive and intrusive punishment component to DRA in order to thin the schedule and also maintain low rates of destructive behavior. A recent replication of this large study reported somewhat more favorable outcomes, but DRA plus schedule thinning still only maintained a 90% reduction from baseline in 11 of 23 applications (48%).²³ In addition, other recent studies have found that when participants treated with DRA were subsequently exposed to extinction of the FCR (or thin reinforcement schedules), treatment relapse often occurred in the form of resurgence of destructive behavior.²⁴⁻²⁶ Similarly, in the first large scale study examining the prevalence of resurgence during schedule thinning, we found that resurgence occurred in 19 out of 25 applications or 76%.²⁷ Collectively, the limitations stated above are evidence for continued refinement to DRA procedures to increase efficacy. In the same way, it is imperative that we develop more durable procedures that will reduce the likelihood of resurgence (i.e., relapse of destructive behavior). These limitations of DRA are actually predicted by a quantitative model derived from behavioral momentum theory. Behavioral momentum theory is a quantitative theory that predicts that DRA, as it is typically implemented, actually promotes resurgence and resistance to extinction for destructive behavior when the FCR is exposed to extinction or thin reinforcement schedules. More importantly, behavioral momentum theory provides clear quantitative guidance on how DRA procedures might be altered in order to mitigate or prevent treatment relapse.²⁸ Several lines of research have used behavioral momentum theory as a guide to develop more efficacious DRA procedures. Unfortunately, recent developments suggest that behavioral momentum theory may not

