1.2 Research Significance

Resurgence as Choice theory is based on two well-developed concepts: (a) Individuals allocate proportionally more behavior towards responses that proportionally produce more reinforcement, and (b) the value of different experiences with reinforcers decreases over time. The theory is relatively more parsimonious than behavioral momentum theory and provides more general predictions than behavioral momentum theory.³² In essence, the theory is grounded in the notion that relapse of behavior is governed by the same processes that underlie choice behavior (e.g., destructive behavior and appropriate communicative responses).³² The two predictions that are most relevant to our project are (a) resurgence of destructive behavior will decrease with increased DRA treatment duration, and (b) reinforcement schedule thinning show included slow, small decreases in reward deliveries (smaller than those previously reported in the literature). Accordingly, our project will examine the effects of different durations of DRA on resurgence and the effects of adjusting the schedule of reinforcement for each session to include slow and small decreases to avoid resurgence. Findings from this project could have vast clinical implications in that we will demonstrate that time in treatment affects relapse and that schedule thinning can be accomplished without recurrence of destructive behavior.

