DRA schedule thinning. Following an initial demonstration of the efficacy of DRA in which the participant is taught the FCR to access the reinforcer maintaining problem behavior, we will initiate DRA schedule thinning by introducing and then systematically lengthening periods of time in which that reinforcer is unavailable. Periods in which the reinforcer is available and unavailable will be signaled using strategies most relevant to the child's treatment and skill-level, such as different colored stimuli (e.g., green and red wristbands), the presentation and absence of work materials, or the presentation and absence of the communication materials. For schedule-thinning steps, we will use the quantitative models of RaC Theory and the results of a corresponding study with nonhuman animals to dynamically adjust each upcoming schedule-thinning step. We will use additional teaching procedures (e.g., prompting, blocking) as necessary to facilitate schedule thinning, as we would clinically. DRA schedule thinning will continue until the stability criteria specified for Experiment 1 are met under terminal schedules that are similar to those found within our control group. We will then compare these data to a control group consisting of the published data depicted in Briggs et al.²⁷ and reviewed by Saini et al.⁴² We will compare our results from the test group in the current study to the published data to determine whether RaC-informed schedule thinning substantially reduced resurgence compared to traditional schedule-thinning methods published in the literature.

B. Data Points

Dependent variables and measurement. The primary dependent measure will be the rate of destructive behavior (aggression, property destruction, self-injurious behavior) assessed via direct observation. Aggression will be defined as forceful pushing or striking others with body parts (e.g., pushing, hitting, kicking, head-butting), hitting others with objects or throwing objects at others, pinching, scratching, or biting. Property destruction will be defined as forceful banging, throwing, overturning, tearing or climbing on objects not made for that purpose. Self-Injurious Behavior will be defined as forceful striking, scratching, rubbing, poking or biting ones own body parts such that

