1.5 Sample Size Justification

With a minimum expected reduction in the per-case prevalence of 50% across 12 participants, we estimate a power of 0.89 with alpha=0.05. In addition, on a per-schedule-step basis, the power increases to 0.98 with alpha=0.05. We will assess the adequacy of RaC and BMT in describing the data.

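### Experiment 2's per-step Fisher test treats repeated thinning steps within a child as independent and counts steps that are smaller by design in the RaC group; its stated power of 0.98 has no support

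*SAP*

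**What the plan says.** The SAP (Statistical Plan, Experiment 2) plans two comparisons between RaC-informed thinning and a published control group: "We will calculate odds ratios for the likelihood of resurgence with and without RaC information on a per-case and on a per-schedule-step basis". Both use Fisher's "exact-probability statistic to test the significance of the odds ratios". After a per-case power of 0.89 for 12 participants it adds: "In addition, on a per schedule-step basis, the power increases to 0.98 with alpha=0.05". Protocol section 1.5 repeats this ("on a per-schedule-step basis, the power increases to 0.98 with alpha=0.05"). Neither document gives a step count, a step-level resurgence rate, a step-level effect or a within-child correlation.

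Three other places in the protocol bear on the point:

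- Section 1.2 says RaC thinning should use "slow, small decreases in reward deliveries (smaller than those previously reported in the literature").
- Section 1.3 A (DRA schedule thinning) says each step is adjusted dynamically and thinning continues until responding is stable "under terminal schedules that are similar to those found within our control group".
- Section 4.3 C says "we will recruit 10 and retain 9 children for Study 2", not 12.

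**The concern.** Fisher's exact test needs independent observations. Steps within one child share that child's history, and in the RaC group each step is set from the same child's recent responding. The plan has no child-level term, cluster adjustment or per-child summary. If steps within a child are positively correlated, the per-step p-value is too small.

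The second fault remains even with no correlation. If RaC steps are smaller and the end point is similar, a RaC child should pass through more steps. This is an inference, since no counts are given, but it follows from sections 1.2 and 1.3 A. A step is then not the same unit in the two groups: cutting one path into more pieces enlarges the RaC denominator and pushes the odds ratio below 1 with no child better off.

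At stake is the reading of Experiment 2. Neither test is named as confirmatory, and the per-step test carries the higher advertised power. Protocol section 1.10 makes a favourable Study 2 the basis for proposing a randomized trial.

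**Working it through.** **1. The stated 0.98.** It cannot be reproduced, because none of its step-level inputs is given. Assume independent steps, 12 RaC and 25 control cases, equal steps per case and a halved step rate. Power of at least 0.98 then needs about 55, 25, 16, 11 or 8 steps per child at control step rates of 10%, 20%, 30%, 40% or 50%. So 0.98 is attainable under some assumptions, but with correlated steps it is too high for an analysis that respects clustering. Illustration with 10 steps per child and step rates of 40% versus 20%, dividing the step count by the design effect 1 + (10 − 1) × ICC (ICC = intraclass correlation within a child):

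| ICC | Design effect | Power, 12 RaC children | Power, 9 RaC children |
|---|---|---|---|
| 0 | 1 | 0.98 | 0.95 |
| 0.05 | 1.45 | 0.91 | 0.84 |
| 0.10 | 1.90 | 0.81 | 0.72 |
| 0.20 | 2.80 | 0.64 | 0.54 |
| 0.30 | 3.70 | 0.51 | 0.42 |

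**2. The denominator effect by hand.** Let every child in both groups have exactly one step with resurgence. Give 25 controls 5 steps each and 10 RaC children 10 steps each. The counts are 10/100 and 25/125.

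Odds ratio = (10/90) ÷ (25/100) = 0.44; Fisher p = 0.043.

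With 9 RaC children (9/90) the odds ratio is again 0.44 and p = 0.058. With two such steps per child the odds ratio is (20/80) ÷ (50/75) = 0.375, with p = 0.0014 for 10 RaC children and 0.0019 for 9. Nothing differs per child in any of these.

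**3. Simulation inputs.** From the protocol: control prevalence (section 1.1: "resurgence occurred in 19 out of 25 applications or 76" percent) and 9 or 10 RaC children (section 4.3 C). Assumed: 25 control cases, 5 or 10 control steps per case, ICC 0 to 0.3, and 1.5 to 2 times as many RaC steps. Steps within a case are beta-binomial with mean p and ICC ρ; 6,000 trials per setting; two-sided Fisher test at 0.05.

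The control step rate p for m steps solves

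P(no resurgence) = ∏ (i = 0 to m − 1) [(1 − p)(1 − ρ) + iρ] / [(1 − ρ) + iρ] = 1 − 0.76 = 0.24.

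At ρ = 0 this is (1 − p)^m = 0.24, so p = 1 − 0.24^(1/5) = 0.248 for 5 steps and 1 − 0.24^(1/10) = 0.133 for 10. At ρ = 0.1, 0.2 and 0.3, p is 0.298, 0.347 and 0.398 for 5 steps and 0.189, 0.244 and 0.300 for 10.

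**4. Clustering alone** (equal steps, no effect). Type I error:

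- ICC 0: 3%–4%
- ICC 0.1: 8%–15%
- ICC 0.2: 12%–23%
- ICC 0.3: 17%–30%

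**5. More RaC steps, no benefit by two definitions.**

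| Scenario | RaC steps vs control | Per-step odds ratio | Per-step test |
|---|---|---|---|
| 76% of children resurge in both groups | 2× | 0.46–0.71 | favours RaC in 38%–58% |
| 76% of children resurge in both groups | 1.5–1.6× | 0.59–0.81 | favours RaC in 20%–31% |
| Equal expected episodes per child | 2× | 0.38–0.46 | rejects in 59%–80% |
| Equal expected episodes per child | 1.5–1.6× | 0.50–0.63 | rejects in 23%–58% |

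In the 76% scenario the per-case Fisher test rejects in 2%–3% of trials. One cell by hand (ICC 0, 10 versus 5 steps): (0.133/0.867) ÷ (0.248/0.752) = 0.46. At ICC 0.3 the same comparison has 10 × 0.300 = 3.0 expected episodes per RaC child against 5 × 0.398 = 2.0 per control, and the odds ratio still favours RaC.

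**The case against.** The strongest points on the other side, and what stands of each:

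- **The equal-episodes figures overstate harmlessness.** In that scenario the share of RaC children with any resurgence also falls, to 59%–75%, so part of the 59%–80% rejection reflects a real per-case difference. This stands. The 76%-in-both rows are the ones to rely on.
- **Small steps are the treatment, so lower risk per step is an intended effect.** True, but section 1.2 seeks thinning without recurrence over the whole path, and a rate per step cannot separate that from a finer division of the path. A child random effect would address clustering but not this.
- **The per-case test may not be clean.** The 76% refers to applications, and one child could contribute more than one. This stands as a caution about the control data, and the simulation treats the 25 as independent.
- **Every size depends on assumed step counts and correlations, and the control group may exceed 25.** This also stands: confidence is high in the principle, not in any one percentage.
- **The consequence is limited.** Both odds ratios are planned, so equal per-case prevalence would appear beside a per-step finding, and the Study 2 endpoint in section 1.3 D is stable responding. This lowers the severity but does not make the per-step p-value valid.
- **Section 1.3 A allows Experiment 1 children to enter Experiment 2.** That does not reconcile 12 participants with the explicit 10 and 9 in section 4.3.

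**Conclusion.** The concern holds. The per-step Fisher test is wrong as written on two separate grounds: it ignores clustering within children, and it uses a denominator that is larger by design in one group. Under the stated assumptions, clustering alone gives a type I error of 8%–30% at ICC 0.1 to 0.3. With the same 76% of children resurging in both groups, the test declares in favour of RaC in 20%–58% of trials, depending on whether RaC children take 1.5 or 2 times as many steps. The 0.98 is unsupported rather than shown to be miscalculated, and it follows a power statement for 12 participants when 9 to 10 are planned. The per-case test is free of the step-count fault, so this should be fixed but does not undermine all of Experiment 2.

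**What to change.** In the SAP, make the per-case comparison the only Fisher test and name it the confirmatory analysis for Experiment 2. Report the per-step odds ratio descriptively, without a p-value, beside the number of steps per case in each group. Withdraw the 0.98 from the SAP and protocol section 1.5, or re-derive it for 9 to 10 children from a stated step count, step-level rate and ICC.

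If inference beyond any versus no resurgence is wanted, compare resurgence episodes per child over the whole path from dense to terminal schedule, using a permutation test that reassigns whole cases. Do not adjust for step size, since small steps are the mechanism under test. In simulation this test rejected in 3%–6% of trials with identical groups and 4%–10% with 1.5 to 2 times as many RaC steps and equal expected episodes. It answers a different question from the per-case test: with 76% resurging in both groups it rejected in about 4%–26% of trials, almost always against RaC, because expected episodes per child then do differ (3.0 versus 2.0 in the example above).

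**Cost.** The per-case change is wording only. The 0.98 claim is lost and intervals widen. The episodes analysis needs published control data by case; if these cannot be recovered, use the per-case test alone. That test is weak at this size: for 76% versus 38% (a halving) against 25 controls, power is 0.47 with 9 children and 0.46 with 10 (0.53 and 0.43 if the control is fixed at 19/25). The report should say so.
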